6.1.2 Prior and Concomitant Medications/Treatments

6.1.2.1 Prior and Concomitant Medications/Treatments for Placebo Data

For the Placebo data as specified in Section 3.2, the prior and concomitant medications are defined the same way as in the Core Study SAP.

6.1.2.2 Prior and Concomitant Medications/Treatments for AL002 Dosed Participants

For participants who are ever exposed to AL002, a medication will be considered as "*prior*" if the end date of administration is before the first dose date of AL002 as specified in Section 3.2.

Any medication with a start date prior to or on the first dose date of AL002 and continued after the first dose date of AL002 or started after the first dose date of AL002 but prior to or on the last dose date of AL002 as specified in Section 3.2 will be considered concomitant medications. Medications started and stopped on the same day as the first dose date or the last dose date of AL002 will also be considered concomitant. Medications with an end date prior to the date of first dose date of AL002 or a start date after the last dose date of AL002 will be excluded from the concomitant medication summary. If a partial end date is entered, any medication with the month and year (if day is missing) or year (if day and month are missing) prior to the first dose date of AL002 will be excluded from the concomitant medication summary. If a partial start date is entered, any medication with the month and year (if day is missing) or year (if day and month are missing) after the last dose date of AL002 will be excluded from the concomitant medication summary. Medications with completely missing start and end dates will be included in the concomitant medication summary, unless otherwise specified.

The World Health Organization Drug Dictionary (WHO DD), version March 2020 or newer, will be used to classify prior and concomitant medications by therapeutic class and drug name.

6.1.2.3 Uncoded Medication

All medications are expected to be coded by the anatomic therapeutic class (ATC) for the interim and final analyses. Any uncoded records as of the data cutoff for analysis will be assigned the string "UNCODED" as the anatomic therapeutic class (ATC) code, and the verbatim term will be used as the preferred term (PT), so they can be included in the summary tables.

6.1.2.4 Multiple ATC Assignments

If there are multiple ATC codes assigned to the same concomitant medication, the "primary" one based on a Sponsor authorized medical code will be used.

6.2 Safety Endpoints and Variables

Safety variables include the following:

- AEs, AESIs, and SAEs
- C-SSRS
- CFBs in hematology and chemistry
- CFBs in urinalysis
- CFBs in coagulation
- CFBs in ECG
- CFBs in vital signs
- MRI abnormalities

- CFBs in neurological examination
- CFBs in ophthalmological examination
- CFBs in physical exam

6.2.1 Extent of Exposure to Study Drug and Treatment Compliance

In the LTE Study, all participants will receive intravenous (IV) administration of AL002 on LTE Study Day 1 and then q4w (every 4 weeks) for a minimum 13 doses over a 48-week period, according to the Schedules of Assessments in the LTE protocol.

For Integrated Analysis, definitions are as follows. For LTE Analysis, these definitions are restricted to exposure, doses and compliance at and after first AL002 dose in the LTE Study.

Duration of Exposure

Duration of exposure (day) is defined as the total number of days that a participant is exposed to any amount of study drug (AL002 or placebo), regardless of any temporary interruptions in study drug administration,

For integrated analysis, duration of exposure (days) = $\min(\text{last dose date} + 28, \text{death date} + 1) - \text{first dose date}$ in the core study, where the first and last dose date of study drug are defined in Section 3.2. 28 days (q4w) is the study drug administration (IV) interval.

The first and last dose dates of placebo are the same as those dates in the Core study.

Duration of exposure (week) is defined as the duration of exposure to study drug in days divided by 7.

Duration of exposure (month) is defined as the duration of exposure to study drug in days divided by 30.4375.

Duration of exposure (years) is defined as the duration of exposure to study drug in days divided by 365.25.

Duration of Exposure to AL002

Duration of exposure to AL002 is defined as above for duration of exposure to study drug, but placebo is excluded from the definition.

Duration of LTE Exposure to AL002

Duration of exposure to AL002 (day) in the LTE Study will be calculated as

Duration of exposure (days) = $\min(\text{last dose date} + 28, \text{death date} + 1) - \text{first dose date}$ in the LTE study.

Total Number of Doses Received

The total number of study drug doses received is defined as the total number of doses of any amount of study drug that a participant received as recorded on the Exposure – IV electronic CRF.

Treatment Compliance

Treatment compliance is defined as the total cumulative received IV volume of study drug (mL) divided by the total cumulative expected IV volume (mL), and then multiplied by 100. The total cumulative expected IV volume will be the sum of the expected IV volume while they are on study treatment across all planned study days, up to the date of withdrawal, if participant discontinued study drug early. For compliance during the LTE Study, compliance is restricted to LTE visits.

The formula for calculation is as follows:

$$\text{Treatment Compliance} = 100 \times \frac{\text{total cumulative received IV volume (mL)}}{\text{total cumulative expected IV volume (mL)}}$$

6.2.2 Adverse Events

All AEs will be collected after the participant signs the informed consent form. AEs will be characterized by seriousness, special interest, severity, relationship to study drug, and outcome.

AEs will be collected and coded by system organ class (SOC) and PT using MedDRA, Version 23 or newer.

6.2.2.1 Treatment-Emergent Adverse Events

6.2.2.1.1 *Treatment-Emergent Adverse Events for Placebo Data*

For the Placebo Data as specified in Section 3.2, the treatment-emergent AEs (TEAEs) are defined the same way as in the Core Study SAP. And handling of incomplete dates is specified in the Core Study SAP.

6.2.2.1.2 *Treatment-Emergent Adverse Events for AL002 Dosed Participants*

For participants who were ever exposed to AL002, AEs that occur on or after the first dose date of AL002 and up to 90 days after study drug discontinuation will be considered TEAEs.

- If both the start time of the AE and the time of the first AL002 administration are available, an AE is considered a treatment-emergent AE (TEAE) if its start date and time are on or after the first AL002 administration and no later than 90 days after the last dose date of AL002. The last dose date of AL002 is defined in Section 3.2.
- If either the start time of the AE or the time of the first AL002 administration is unavailable, an AE is considered a TEAE if its start date is on or after the first dose date of AL002 and no later than 90 days after the last dose date of AL002. Handling of incomplete dates is specified in Section 6.2.2.6.

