### 7.1. Definition of Adverse Event

AEs are any untoward medical occurrence in a participant enrolled into this study, including side effects, injury, toxicity, sensitivity reaction, intercurrent illnesses, clinically significant physical exam signs, or sudden death, whether or not it is considered related to the study drug.

Participants will be instructed to contact the Investigator at any time after informed consent if any symptoms develop. Participants will be instructed to report all AEs to the Investigator. All AEs must be appropriately documented in the participant's original source documents and on the eCRFs. Investigators should report the diagnosis rather than list symptoms, whenever possible.

A treatment-emergent AE is defined as any event not present before exposure to study drug and/or radiotracer, and any event that worsens from baseline after exposure.

Adverse events resulting from concurrent illnesses, reactions to concurrent illnesses, reactions to concurrent medications, or progression of disease states must also be reported within the established time frames.

An AE does not include the following:

- Elective medical or surgical procedures planned prior to the start of study drug (eg, hip replacement surgery) that did not result from a worsening of a pre-existing condition (ie, prior to signing informed consent). Note: Any serious procedural complication or hospital-emergent conditions (eg, nosocomial infection) that, for instance, prolongs the hospitalization would be reported as an SAE.
- Any medical condition or clinically significant laboratory abnormality that has an onset date before the consent form is signed, and that is not related to a protocol-associated procedure, is not an AE. A pre-existing condition should be reported as an AE only if its frequency, intensity, or symptoms worsen during the course of the study.
- Situations where an untoward medical occurrence has not occurred (eg, hospitalization for study drug administration per institutional guidelines, elective surgery, social and/or convenience admissions).

Disease progression within expected parameters for the study population is not considered an AE. See [Section 7.3.1](#) for Protocol-Specific Disease Progression Adverse Event and Serious Adverse Event Reporting Requirements.

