**Table 6: Adverse Event Grading Criteria**

Grade	Severity	Description
1	Mild	Asymptomatic or mild symptoms; clinical or diagnostic observations only; intervention not indicated
2	Moderate	Minimal, local, or noninvasive intervention indicated; limiting age-appropriate instrumental ADL a
3	Severe or medically significant but not immediately life-threatening	Hospitalization, or prolongation of hospitalization indicated; disabling, limiting self-care ADL b
4	Life-threatening consequences	Urgent intervention indicated
5	Death	Death related to AE

ADL=activities of daily living, AE=adverse event.

a Instrumental ADL refer to preparing meals, shopping for groceries or clothes, using the telephone, managing money, etc.

b Self-care ADL refer to bathing, dressing and undressing, feeding self, using the toilet, taking medications, and not bedridden.

Note that “severity” is a measure of intensity and that a severe AE is not necessarily an SAE.

Changes in the severity of an AE should be documented to allow assessments of the duration of the events at each level of intensity. AEs characterized as intermittent do not require documentation of onset and end date of each episode. When the intensity of an AE changes more than once a day, the maximum severity for the event should be recorded for that day. If the intensity changes over a number of days, these changes should be recorded separately (eg, as having distinct onset dates on one or more eCRF lines).

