### **7.7. Reporting Adverse Events**

#### **7.7.1. Adverse Events and Serious Adverse Events Reporting**

Regardless of cause or relationship to study drug, all AEs/SAEs that occur after a participant signs the ICF until the EOS participation, regardless of clinical significance or of the suspected relationship of the AE to study drug and/or radiotracer, should be reported by the Investigator. All unresolved AEs and/or SAEs will be followed through their resolution, or until the participant returns to his or her baseline condition, or is lost to follow-up or dies of another cause. Additionally, SAEs considered related to the study drug or radiotracer, which occur at any time during the study, should be reported by the Investigator, regardless of the AE/SAE collection window. Definitions pertaining to AEs are provided in [Section 7.1](#) and descriptions of AE grading criteria are provided in [Table 6](#).

Information to be collected includes but is not limited to the following:

- Event term
- Time and date of onset of event
- Investigator-specified assessment of severity and relationship to study drug or radiotracer
- Time and date of the end of the event or the date on which the event changes severity
- All serious criteria (if applicable)
- Any required treatment or evaluations
- Event outcome

In the event of any SAE reported or observed during the study, the site is required to complete the AE eCRF within the EDC system, including the event seriousness criteria, within 24 hours of becoming aware of the event or aware of substantive new information relating to the event.

Please note 2 additional scenarios requiring 24-hour reporting to the Sponsor:

1. AEs assessed as *related* to the *radiopharmaceutical*, Neuraceq® (florbetaben F18 injection). **Please note:** *if the site's imaging facility is located outside of the institutional facility, please ensure the imaging lab is aware of this requirement.*
2. Special situations (eg, overdose, occupational exposure, medication error) associated with Neuraceq® **or** the Alector study drug *regardless of whether the special situation is associated with an AE and regardless of the Investigator's causality assessment of the event to the radiotracer or Alector study drug.*

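### The SAP classifies a TEAE on AL002 by start date alone and drops the protocol's test of worsening from baseline, so some events that began before AL002 can be misclassified, chiefly in the Titration Cohort

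*SAP*

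**What the plan says.** SAP 6.2.2.1.2 covers everyone ever exposed to AL002. Where clock times are missing, "an AE is considered a TEAE if its start date is on or after the first dose date of AL002" and falls no later than 90 days after the last one. Where times are known, the same test is applied to date and time. Grade, seriousness and prior status play no part. For Group P-TC the first AL002 dose is LTE Day 1 (SAP 3.2).

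Protocol 7.1 defines a treatment-emergent AE as "any event not present before exposure to study drug and/or radiotracer, and any event that worsens from baseline after exposure".

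On recording, the text below Table 6 in Protocol 7.5.1 says that when intensity changes over a number of days, "these changes should be recorded separately (eg, as having distinct onset dates on one or more eCRF lines"). It does not confine this to worsening. It adds that "AEs characterized as intermittent do not require documentation of onset and end date of each episode". Protocol 7.7.1 lists among the items to be collected: "Time and date of the end of the event or the date on which the event changes severity".

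On events already present at entry, Protocol 7.1 says: "A pre-existing condition should be reported as an AE only if its frequency, intensity, or symptoms worsen during the course of the study".

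SAP Section 1 gives the SAP precedence where it differs from the protocol.

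**The concern.** The two definitions are not equivalent, and the one that governs has lost the baseline comparison. That matters because a start date in the AE data may mark a change of grade rather than the start of the event, and because some events may keep an old start date although they became worse on drug.

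The Titration Cohort is the group most exposed. Its participants reach their first AL002 dose after a period on placebo, with LTE adverse events already being collected from consent, so an event can straddle that dose. Group T-T had its first AL002 dose in the Core Study and has no placebo period before it.

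At stake are the treatment-emergent tables in SAP 7.4.3 for the Titration Cohort and for the AL002 total group that pools it. SAP Table 2-1 names AESI and SAE incidence as Part 1 primary endpoints, and SAP 7.4.3 tabulates both as treatment-emergent events. In the integrated tables the placebo column follows the Core Study SAP's TEAE definition, which is not supplied, so it cannot be confirmed that placebo and AL002 columns use the same rule.

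**Working it through.** The plan gives no figure to reproduce. The check applies both definitions to the same record patterns.

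**Inputs**
- First AL002 dose at day 0, which is LTE Day 1 for the Titration Cohort (SAP 3.2).
- 13 doses every 4 weeks (SAP 6.2.1), so the last dose is 12 × 28 = 336 days after the first, and the window closes at 336 + 90 = 426 days.
- SAP rule: a line is a TEAE if 0 ≤ start ≤ 426.
- Protocol rule: new after day 0, or worse than at baseline.
- Pre-dose onset placed at day −20, inside the screening/baseline period of up to 4 weeks (Protocol 3.2.1).

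| Pattern | Line start(s) | SAP | Protocol |
|---|---|---|---|
| New event after dose | 30 | yes | yes |
| Grade 3 eases to Grade 1 at day 10, new line | −20, 10 | **yes** | **no** |
| Grade 3 eases to Grade 1 at day 10, one line | −20 | no | no |
| Grade 1 worsens to Grade 3 at day 10, new line | −20, 10 | yes | yes |
| Grade 1 worsens to Grade 3 at day 10, one line | −20 | **no** | **yes** |
| Intermittent, worse after dose, no episode dates | −20 | **no** | **yes** |

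The definitions disagree in 3 of 6 patterns: one false positive and two misses. This counts patterns and says nothing about how often each occurs.

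**Does a later rule repair this?** SAP 6.2.2.6 handles only incomplete dates. SAP 7.4.3.1 reduces repeated or changing events to one count at the worst grade, but does not ask whether the event pre-dates AL002. For Group P-TC those rules run separately for placebo and for the Titration Cohort, so one split event can appear in both columns. For the LTE Analysis, SAP 6.2.7.1.3 does not count ARIA-E already present at LTE Baseline as new, but that belongs to the MRI analysis; the AE tables have no counterpart.

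**How far back does the false positive reach?** LTE adverse events are collected from LTE consent. Under Protocol 7.1 a condition with onset before consent is reportable only if it worsens, so one that merely eases should produce no LTE line. Within the LTE protocol the false positive is therefore clear only for onsets between LTE consent and LTE Day 1, up to 4 weeks. For older placebo-period events it depends on the AL002-2 recording rules, which are not supplied.

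**Scale of one error.** The documents give neither AE counts nor the size of the Titration Cohort. Assume, for illustration only, that it is a quarter of the 176 to 198 participants expected in SAP 3.5: 0.25 × 176 = 44 and 0.25 × 198 = 49.5. One misclassified participant with no other TEAE then moves the any-TEAE percentage by 100/49.5 = 2.0 to 100/44 = 2.3 points. The number of such participants cannot be derived.

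**The case against.** The strongest reply has four parts.

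*Line splitting is not certain.* Protocol 7.5.1 gives distinct onset dates as an example and allows one or more lines, and the date of a severity change could be held without replacing the event's start date. The annotated CRFs are not supplied. This stands: both errors are conditional on how the lines are built.

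*For an ordinary event, one convention cannot produce both errors.* If every change opens a new dated line, worsening is caught and only easing is miscounted. If none does, easing is harmless and only worsening is missed. This also stands. The two errors occur together only through intermittent events or mixed practice between sites. But neither convention makes the SAP rule agree with the protocol.

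*Protocol 7.1 already screens out old conditions.* A reader might infer that up to 96 weeks of placebo-period events flow into the AL002 column whenever they ease. The documents do not support that, because an event with onset before LTE consent is an LTE AE only if it worsens.

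*The titration question is unaffected.* A reader might infer that the slower-versus-faster comparison is biased. It is not affected: SAP 7.4.8 compares ARIA events among participants with evaluable MRI scans, and SAP 6.2.7 takes its ARIA events from MRI worksheet readings. The TEAE flag does not enter.

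What remains is the missing limb in a definition that overrides the protocol.

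**Conclusion.** The point holds as a mismatch of definitions with a limited and conditional effect. SAP 6.2.2.1.2 omits the worsening-from-baseline test in Protocol 7.1, and nothing downstream restores it. Followed literally, it admits a pre-dose event that only eased on a new dated line, and misses an intermittent or single-line event that worsened on AL002.

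The exposure lies chiefly in the Titration Cohort's TEAE, treatment-emergent SAE and treatment-emergent AESI tables, and through them in the AL002 total. The size cannot be computed from the documents, and any count of affected participants would rest on an assumed frequency. Preferred-term, severity and relatedness tables are more sensitive than the any-TEAE rate, which changes only for a participant with no other TEAE.

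The conclusion rests on reading the SAP rule line by line, as written, and on Protocol 7.5.1 being followed by at least some sites. It should be corrected before lock, but it does not undermine the ARIA titration analysis.

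**What to change.** Reword SAP 6.2.2.1.2 so that a TEAE is either
- an event with first onset on or after the first AL002 dose and no later than 90 days after the last, or
- an event present before the first AL002 dose whose grade or seriousness within that period exceeds its level at baseline, meaning its last status before that dose.

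State that a line continuing a pre-dose event at the same or a lower grade is not a TEAE, and apply the same rule to treatment-emergent SAEs and AESIs.

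The comparator should be the baseline status, as in Protocol 7.1, and not the highest grade ever recorded before dosing. An event at Grade 3 in the Core Study, Grade 1 at LTE baseline and Grade 2 on AL002 has worsened from baseline; a highest-grade test would discard it.

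If a start-date-only rule is intended, the SAP should say so and justify leaving the protocol definition.

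The cost is a paragraph of SAP text and a programming step that links lines of the same event before classification, with ambiguous links reviewed before database lock. Protocol 7.7.1 already calls for the date of a severity change, so much of the information should exist. For intermittent events without episode dates, worsening can be recognised only where a change of grade or seriousness was recorded.

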6.2.2.2 Adverse Events of Special Interest

An AE of special interest (AESI) is a serious or nonserious AE that is of scientific and medical concern specific to a product for which ongoing monitoring and rapid reporting by the Investigator to the Sponsor should occur. AESI for this study are defined as the following occurrences:

- Amyloid-related imaging abnormality – hemosiderin deposits (ARIA-H)
- Amyloid-related imaging abnormality – edema (ARIA-E)

- Uveitis

6.2.2.3 Serious Adverse Events

SAEs will be identified and captured as SAEs for AEs that meet the definition of SAE that is specified in the protocol.

6.2.2.4 Relationship of Adverse Events to Study Drug

Related AEs are those for which the Investigator selected “Related” on the AE electronic CRF to the question whether an event is related to study drug. Relatedness will always default to the Investigator’s choice, not that of the medical monitor.

6.2.2.5 Relationship of Adverse Events to Radiotracers

TEAEs that are related to radiotracers will not be summarized or listed for this LTE Analysis.

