**Statistical Methods:**

All data for participants will be listed as collected. Analyses may combine the data of the parent study with the data of this AL002-LTE study. Missing data will not be imputed, unless otherwise specified in the statistical analysis plan (SAP). The SAP will provide further details regarding the analysis sets and planned analysis methodologies to address all study objectives. Continuous data will be summarized using an [REDACTED]

[REDACTED] unless otherwise specified in the SAP.

Categorical data will be summarized using [REDACTED]), unless otherwise specified in the SAP. For additional information, see [Section 8](#).

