**Table 4: Comprehensive List of Investigational and Auxiliary Medicinal Products (IMP and AMP) Used in AL002-LTE Study**

	Category	Authorization Status
Study Drug (AL002)	IMP	Not authorized for use in any country.
[  F]MK-6240 Tau PET radiotracer	AMP	
Not authorized for use in any country.
 
Will only be used in accordance with approved national and/or local standards; Tau PET will not be conducted in those countries where the Tau PET radiotracer is unavailable and/or where it is not part of the approved Clinical Trial Application.
 
Use of the [F]MK-6240 tracer is justified because this Tau PET tracer has improved tracer characteristics (lower non-specific binding and lower prevalence of off-target binding) as well as the ability to detect lower levels of tau compared to other available tracers, which is important to be able to measure small longitudinal changes in tau levels (Rowe 2022).

[  F]florbetaben (Neuraceq) Amyloid PET radiotracer	AMP	
Authorized for use in US, European Union (including Spain, Poland, Italy, France, Germany, and Netherlands), UK, Canada, and Australia.
 
Neuraceq will be used in accordance with the terms of its marketing authorization in all countries in which it is approved and will not be used in any countries where it is not authorized.

	Category	Authorization Status
[  F]florbetapir (Amyvid) Amyloid PET radiotracer	AMP	Authorized for use in US, UK, Spain, Italy, France and Germany; however this radiotracer is only being used in the AL002-LTE study in the US.  Amyvid will be used in accordance with the terms of its marketing authorization in all countries in which it is approved and will not be used in any countries where it is not authorized.

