## 7. ASSESSMENT OF SAFETY

The Investigator's assessment of the relationship of an AE, SAE, or radiotracer AE to study drug is part of the documentation process, but it is not a factor in determining what is or is not reported in the study. If there is any doubt as to whether a clinical observation is an AE/SAE, the event should be reported.

The Investigator is responsible for reporting all AEs/SAEs/AESI that are observed or reported during the study, from the time a participant signs the ICF until the EOS, regardless of clinical significance or of the AEs suspected relationship to study drug and/or radiotracer.

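### Read literally, SAP 6.2.2.5 takes radiotracer-related TEAEs out of the LTE Analysis tables and contradicts the SAP's own all-AE listing and all-deaths rule

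*SAP*

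**What the plan says.** SAP 6.2.2.5 is a single sentence: "TEAEs that are related to radiotracers will not be summarized or listed for this LTE Analysis". It follows SAP 6.2.2.4, which defines drug-related events by the investigator's answer. SAP 6.2.2 says that "AEs will be characterized by seriousness, special interest, severity, relationship to study drug, and outcome", with no mention of the tracers. For participants ever dosed with AL002, SAP 6.2.2.1.2 says that "AEs that occur on or after the first dose date of AL002 and up to 90 days after study drug discontinuation will be considered TEAEs".

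Protocol 7.1 is wider. It treats as treatment-emergent "any event not present before exposure to study drug and/or radiotracer, and any event that worsens from baseline after exposure". Protocol 7.5.2 has the investigator judge causality for study drug or radiotracer, and Protocol 7.7.1 lists that judgement among the items collected. In Protocol Table 4 the tau tracer, like AL002 itself, has the status "Not authorized for use in any country".

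SAP Section 1 gives the SAP precedence over the protocol. It also separates the LTE Analysis (LTE data, with Core baseline where needed) from the Integrated Analysis (Core and LTE data together).

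**The concern.** Incidence of AEs is a primary endpoint in Protocol Section 2, without exception by cause. An AE table normally holds every event in the window, and attribution is shown as a subset of it. Here a stated rule appears to use attribution to decide whether an event is in the table at all. Nothing in Protocol 7.5.2 makes the drug and tracer answers mutually exclusive, so an event judged related to both would also go. SAP 7.4.3.1 leans the other way: an event with missing drug causality is counted as related.

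At stake are complete LTE safety tables. Only participants who opted into PET could be affected, so any gap would be selective.

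**Working it through.** No power, alpha or rate calculation applies, and the plan states no figure to reproduce. The check sets the relevant sections against the two readings of SAP 6.2.2.5.

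**1. Which displays are touched?** SAP 7.4.3 gives the LTE Analysis five selected summaries: overall AEs, TEAEs by system organ class and preferred term, TEAEs leading to drug interruption, SAEs, and TEAEs leading to death.

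| Display | Literal reading (events removed) | Mild reading (no separate tracer display) |
|---|---|---|
| Five LTE Analysis summaries, SAP 7.4.3 | Tracer-related events missing | Complete |
| By-participant listing of all AEs, SAP 7.4.3 | Contradicted | Complete; tracer column not specified |
| All deaths summarized and listed, SAP 7.4.3.2 | Contradicted for a tracer-related death | Complete |
| Integrated TEAE summaries, SAP 7.4 and 7.4.3 | Not named in the exclusion, so complete | Complete |
| ARIA analyses, SAP 6.2.7 and 7.4.8 | Unaffected: built from central-reader worksheets | Unaffected |

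**2. Do LTE-period events reach the Integrated Analysis?** Yes. SAP 7.4 makes it the default for safety, in the Non-e4/e4 Set. SAP 5.2.2 says no e4/e4 participant entered the LTE. SAP 7.4.1.2 includes all Core and LTE data.

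**3. Would the two analyses agree?** Not under the literal reading. A Titration Cohort participant's first AL002 dose falls on LTE Day 1, and SAP 7.4.3.1 counts that cohort's LTE events separately from its placebo events. The cohort's LTE and Integrated TEAE tables therefore cover the same events, yet would differ by the tracer-related ones with no explanation.

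**4. Against the protocol.** The protocol anchors treatment emergence to drug and/or tracer; the SAP anchors it to AL002 alone and then excludes on tracer attribution. The anchor matters separately. An event after an LTE baseline PET scan, before the first AL002 dose in a former placebo participant, can be treatment-emergent under Protocol 7.1 but not under SAP 6.2.2.1.2. It falls in the Placebo Data, whose TEAE rule is in the Core Study SAP, which was not available.

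**5. Scale.** Neither document gives the number of tracer-related AEs or of PET participants. Two bounds can be had:
- Scheduled exposure: SAP Tables 7-33 and 7-35 allow baseline plus two later scans per tracer, so at most 3 + 3 = 6. If both baselines are reused from within 24 weeks in the parent study (Protocol 3.2.1), it is 2 + 2 = 4. These are opportunities for an event, not events.
- Effect of one removal: SAP 3.5 expects 176 to 198 participants. Assuming all are dosed, one participant lost from a row of the total AL002 column moves it by 1/198 = 0.51 to 1/176 = 0.57 percentage points, and by more in a single-arm column. An any-TEAE row moves only if that participant has no other TEAE.

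**The case against.** The strongest defence is that SAP 6.2.2.5 never removes anything. It sits beside 6.2.2.4, which sets up the drug-related category tabulated in SAP 7.4.3, and it may say only that there is no matching tracer-related category. SAP 7.4.3 indeed lists none, and neither the TEAE definition nor the counting rules carry a tracer exclusion. This reading is plausible. It does not settle the matter, because the sentence speaks of the events themselves and says they are not listed, while SAP 7.4.3 lists all AEs. A programmer has to guess.

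A reader might infer that tracer-related events vanish from the safety report and bias the primary endpoint downward. The documents do not support that. The exclusion names only the LTE Analysis, and the main safety tables are Integrated. If the phrase was meant loosely for the whole SAP the loss would be wider, but the SAP's own definition points to the narrower scope. ARIA results do not depend on investigator attribution.

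A reader might also infer that the judgement is made blind. Protocol 5.4.1 blinds treatment assignment; no blinding to PET tracer is described, and everyone dosed in the LTE receives AL002.

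Two protocol statements give less support than they seem to. The clause on causality, "but it is not a factor in determining what is or is not reported in the study", concerns relationship to study drug and what sites report. The synopsis promise, "All data for participants will be listed as collected", is followed by a deferral of planned methods to the SAP. Site collection, 24-hour reporting of events related to the amyloid tracer florbetaben (Protocol 6.3.1 and 7.7.1) and data monitoring committee review (Protocol 12.1.1) are unchanged.

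**Conclusion.** The point holds as a conflict in a stated rule, confined to the LTE Analysis. Followed as written, SAP 6.2.2.5 yields incomplete LTE tables of AEs, SAEs and deaths. It contradicts SAP 7.4.3 and 7.4.3.2 and departs from Protocol 7.1, with the SAP prevailing over the protocol. If the mild reading is intended, the tables are complete and the defect is wording; even then, no planned display is specified to show the tracer attribution that sites record.

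The size in events is unknown and may be small or zero. The conclusion assumes that LTE Analysis carries its SAP Section 1 meaning. It should be corrected, but nothing in the documents suggests that it would change the trial's overall safety conclusions.

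**What to change.** Replace the sentence in SAP 6.2.2.5 with: *All TEAEs are included in all LTE and Integrated TEAE summaries and listings regardless of relationship to a radiotracer; no separate summary table of radiotracer-related TEAEs is produced.* Show radiotracer relationship as a column in the by-participant listing of all AEs.

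This resolves both readings. The cost is one sentence and one listing column; the variable is already collected. A separate listing by tracer with days since the last scan is optional. The same edit could say whether anchoring TEAEs to AL002 alone is a deliberate departure from Protocol 7.1.
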